Stopping procedures were computed using the sequential probability ratio test (SPRT) with alpha set at .05 and power at 80%. Adverse events were examined based on three categories of (1) severe, (2) moderate requiring oxygen or room air flow, and (3) moderate requiring tactile stimulation. Using baseline rates of 8%, 13%, and 8%, accordingly for categories 1 through 3 above, and excessive rates of 13%, 25%, and 17%, accordingly, stopping procedures were calculated as follows:

- Severe AE
 - Moderate AE (oxygen/flow)
 - Moderate AE (tactile stimulation)
- 1) Using baseline rate of 8% and excessive rate of 13%, the first 5 events would not stop the trial. But the following would require a stop:
 - If 6 of the first 8 patients have a severe adverse event
 - If 7 of the first 17 patients have a severe adverse event
 - If 8 of the first 27 patients (goes out of our sample size) have a severe adverse event
 - 2) Using baseline rate of 13% and excessive rate of 25%, the first 4 events would not stop the trial. But the following would require a stop:
 - If 5 of the first 8 patients have a moderate adverse event requiring oxygen/flow
 - If 6 of the first 13 patients have a moderate adverse event requiring oxygen/flow

Principal Investigator: [name], MPH

Application Number: IRB00107690

- If 7 of the first 18 patients have a moderate adverse event requiring oxygen/flow
- If 8 of the first 24 patients have a moderate adverse event requiring oxygen/flow

3) Using baseline rate of 8% and excessive rate of 17%, the first 3 events would not stop the trial. But the following would require a stop:

- If 4 of the first 6 patients have a moderate adverse event requiring tactile stimulation.
- If 5 of the first 14 patients have a moderate adverse event requiring tactile stimulation.
- If 6 of the first 22 patients have a moderate adverse event requiring tactile stimulation
- If 7 of the first 30 patients (goes out of our sample size) have a moderate adverse event requiring tactile stimulation.

For this trial we define “unsafe” if the use of methadone is associated with frequency of moderate or adverse cardiorespiratory events that requires an intervention that exceeds a specified thresholds outlined above that is sufficient to stop the trial. Thus unsafe and stopping parameters should be the same in this small trial.

e. **Legal risks such as the risks that would be associated with breach of confidentiality:**

N/A

f. **Financial risks to the participants:**

N/A

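### Three of the eleven listed safety-stopping limits are one patient lower than the SPRT they are said to come from, so at two reachable counts the list carries on where the stated test stops

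*Combined protocol and SAP*

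**What the plan says.** Section 7.d (Data Safety and Monitoring Plan) gives the method: "Stopping procedures were computed using the sequential probability ratio test (SPRT) with alpha set at .05 and power at 80" per cent. It then gives a baseline rate, an excessive rate and a starting count for each category:

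- Severe: "Using baseline rate of 8% and excessive rate of 13%, the first 5 events would not stop the trial".
- Moderate, oxygen or flow: "Using baseline rate of 13% and excessive rate of 25%, the first 4 events would not stop the trial".
- Moderate, tactile stimulation: "Using baseline rate of 8% and excessive rate of 17%, the first 3 events would not stop the trial".

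The limits that follow are described as counts that oblige the trial to stop:

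- Severe: 6 of 8, 7 of 17, 8 of 27.
- Oxygen/flow: 5 of 8, 6 of 13, 7 of 18, 8 of 24.
- Tactile stimulation: 4 of 6, 5 of 14, 6 of 22, 7 of 30.

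The three at issue are "If 7 of the first 17 patients have a severe adverse event", "If 7 of the first 18 patients have a moderate adverse event requiring oxygen/flow" and "If 7 of the first 30 patients (goes out of our sample size) have a moderate adverse event requiring tactile stimulation". The same section defines an unsafe treatment by these thresholds. The methadone group is planned at 25 infants (Accrual paragraph; 13 plus 12 in section 7.d).

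**The concern.** Alpha, power and the two rates fix an SPRT limit completely, so each entry can be checked without any outside figure. For a given number of events, the limit is the largest number of infants at which that count still crosses the upper boundary. A listed number below that value makes the criterion harder to meet: the trial goes on at a count where its own test says stop. Here the delay would be in stopping for harm in newborns, in a list that also serves as the plan's definition of unsafe.

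**Working it through.** **Inputs (all from section 7.d).** Alpha 0.05; power 0.80; rates p0 and p1 of 0.08 and 0.13 (severe), 0.13 and 0.25 (oxygen/flow), 0.08 and 0.17 (tactile).

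**Boundary.** Wald's upper limit is ln(power/alpha) = ln(0.80/0.05) = ln 16 = 2.7726.

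**Rule.** With k events in n infants, stop if

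k·a − (n − k)·c ≥ 2.7726, where a = ln(p1/p0) and c = ln((1 − p0)/(1 − p1)).

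Solved for n, the largest stopping n is k + (k·a − 2.7726)/c, rounded down.

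| Category | a | c |
|---|---|---|
| Severe | 0.48551 | 0.05588 |
| Oxygen/flow | 0.65393 | 0.14842 |
| Tactile | 0.75377 | 0.10295 |

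**Starting counts.** These reproduce. Even if every infant so far has had an event, 5 severe events give 5 × 0.48551 = 2.43, 4 oxygen/flow events give 2.62 and 3 tactile events give 2.26, all below 2.7726.

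**All eleven limits.**

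| Category | Events | Unrounded limit | Rounded down | Listed |
|---|---|---|---|---|
| Severe | 6 | 8.51 | 8 | 8 |
| Severe | 7 | 18.20 | **18** | **17** |
| Severe | 8 | 27.89 | 27 | 27 |
| Oxygen/flow | 5 | 8.35 | 8 | 8 |
| Oxygen/flow | 6 | 13.75 | 13 | 13 |
| Oxygen/flow | 7 | 19.16 | **19** | **18** |
| Oxygen/flow | 8 | 24.57 | 24 | 24 |
| Tactile | 4 | 6.36 | 6 | 6 |
| Tactile | 5 | 14.68 | 14 | 14 |
| Tactile | 6 | 22.9993 | 22 | 22 |
| Tactile | 7 | 31.32 | **31** | **30** |

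**Direct check one infant past the listed limit.** Each value still meets 2.7726:

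- Severe, 7 of 18: 7 × 0.48551 − 11 × 0.05588 = 2.784.
- Oxygen/flow, 7 of 19: 7 × 0.65393 − 12 × 0.14842 = 2.796.
- Tactile, 7 of 31: 7 × 0.75377 − 24 × 0.10295 = 2.806.

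**Could another boundary give the whole list?** No. For "If 6 of the first 8 patients have a severe adverse event" to be a stop, the boundary can be at most 2.8013, the log-likelihood ratio at that count. To exclude tactile 7 of 31, it must exceed 2.8057. No single value does both.

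**Where the numbers probably came from.** Each further event extends the limit by (a + c)/c infants: 9.69, 5.41 and 8.32. Starting from the first limit already rounded down and adding these steps gives:

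- Severe: 8, 17.69, 27.38.
- Oxygen/flow: 8, 13.41, 18.81, 24.22.
- Tactile: 6, 14.32, 22.64, 30.97.

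Rounded down, these are exactly the eleven listed numbers. Carried rounding therefore explains the gap.

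**Effect on the chance of stopping within 25 infants** (exact binomial recursion, checking after every infant):

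| Category | True rate | Listed limits | Exact limits |
|---|---|---|---|
| Severe | 8% | 0.062% | 0.067% |
| Severe | 13% | 1.23% | 1.29% |
| Oxygen/flow | 13% | 1.23% | 1.33% |
| Oxygen/flow | 25% | 25.8% | 26.5% |
| Tactile | 8% | 0.86% | 0.86% |
| Tactile | 17% | 18.3% | 18.3% |

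**The case against.** The best defence is that this is carried rounding of one patient and not a wrong method. Eight entries and all three starting counts are right, and a boundary rounded to 2.8 gives every limit that lies inside the sample. Wald's boundaries only approximate the nominal alpha and power in any case. The 7 of 30 entry cannot apply with 25 infants, and the plan marks it as out of range. The reachable gap is two single points, and the largest change in stopping probability is under 0.8 percentage points. Section 7.d also leaves stopping for harm to the independent monitor's judgment, so a stop at 7 of 18 severe events (39%, against a baseline of 8%) is permitted even though the list does not demand it.

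Most of this stands as a statement of size. It does not make the entries right. The plan states no rounding rule, and no single boundary yields the full list. The monitor's judgment does not correct counts that the section presents as mandatory and uses to define unsafe; the monitor is also told to weigh the strength of the statistical evidence, and this list is the numerical guide supplied.

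**Conclusion.** The point holds. Three of the eleven limits are one patient lower than the stated SPRT gives, and the direction is less protective. Two are reachable: a seventh severe event at exactly infant 18, and a seventh oxygen/flow event at exactly infant 19. The third has no effect at the planned size. The largest change is 0.76 percentage points (25.77% to 26.53%, oxygen/flow at a true rate of 25%), so this is a minor correction.

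The result assumes Wald's standard upper boundary, rates exactly as printed, evaluation after each infant and 25 treated infants. The stopping probabilities treat infants as independent.

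Correcting the entries leaves a separate matter untouched: with only 25 infants, either version stops at the excessive rates with a probability of about 1%, 26% and 18%, well below the stated 80% power.

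**What to change.** In section 7.d, replace 7 of 17 with 7 of 18 (severe), 7 of 18 with 7 of 19 (oxygen/flow) and 7 of 30 with 7 of 31 (tactile stimulation, still outside the sample). Alternatively, print the inequality with its boundary of ln 16 and apply it after each infant, so that the list becomes illustrative. Either change applies only the test the plan already names. It alters three numbers or adds one line, and has no operational cost.

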JHACH admitted and average of 131 NAS infants in recent years who required pharmacological treatment for NAS. Approximately 30% of those mother/infant dyads were residents of PAR. We anticipate to enroll 25 mother/baby dyads into the methadone treatment group and 25 mother/baby dyads into the control group for a total of 100 participants. Both the mother and infant are research participants. Those infant participants are defined as 1) needing methadone or other opiate treatment, 2) transitioning to home care, and 3) successfully weaning off medication.

This number has been extrapolated taken into account the following projections/assumptions: 1) not all mothers staying at PAR will meet criteria for participation, and 2) polydrug use may be discovered at the time of delivery thus excluding from participation, and 3) 20-40% of infants enrolled may need adjunct second line therapy.

b. Blinding, including justification for blinding or not blinding the trial, if applicable.

This is a demonstration study with no blinding of subjects involved.

c. Justification of why participants will not receive routine care or will have current therapy stopped.

All infants will continue to receive routine hospital care. Methadone treatment is approved by the FDA, and endorsed by the AAP for inpatient and outpatient treatment of infants with NAS. While methadone is not used as the standard of care at JHACH NICU for infants with NAS at birth, it is still used for later iatrogenic withdrawal in the NICU and other intensive care units in the hospital.

d. Justification for inclusion of a placebo or non-treatment group. N/A Will need to justify this as a comparison groups has been included

e. Definition of treatment failure or participant removal criteria.

As delineated above, infants will be off-treatment from the demonstration project if 1) they require the addition of a second-line of pharmacological treatment or 2) they require re-admission to the

Principal Investigator: [name], MPH

Application Number: IRB00107690

hospital. Data will still be collected until final hospital discharge for these infants and the maternal assessments of bonding and depression will remain ongoing. .

Other Indications for participant off-study:

- a. Parent withdraws informed consent at any time
 - b. Infant transfers to another hospital.
 - c. Infant experiences an unexpected adverse event deemed related to study intervention

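### Section 7.d defines unsafe only as crossing the SPRT stopping limits, so the trial can end with 7 of 25 infants (28%) having a severe event and not meet that definition

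*Combined protocol and SAP*

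**What the plan says.** Section 7.d of the protocol describes the limits: "Stopping procedures were computed using the sequential probability ratio test (SPRT) with alpha set at .05 and power at 80" percent. There are three event categories, each with a baseline and an excessive rate: severe (8% and 13%), moderate needing oxygen or flow (13% and 25%), and moderate needing tactile stimulation (8% and 17%).

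For severe events the section states: "Using baseline rate of 8% and excessive rate of 13%, the first 5 events would not stop the trial". It then lists three limits. Two lie within the planned group size: 6 events by infant 8, and 7 events by infant 17. The third lies beyond it: "If 8 of the first 27 patients (goes out of our sample size) have a severe adverse event".

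The same section calls methadone unsafe if the frequency of cardiorespiratory events needing intervention "exceeds a specified thresholds outlined above that is sufficient to stop the trial", and concludes: "Thus unsafe and stopping parameters should be the same in this small trial".

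The Accrual text gives the group size: "We anticipate to enroll 25 mother/baby dyads into the methadone treatment group". Adverse events are collected only in infants who receive the study drug (section 7, Adverse Events), so the denominator is 25 and there is no concurrent comparison. Section 6 (Study Statistics) plans no adverse-event analysis. Apart from the limits, section 7.d leaves stopping for harm to an independent monitor's judgment, with reviews after 13 infants, after the next 12, and at completion.

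**The concern.** A stopping limit answers whether the evidence so far is strong enough to halt accrual. A statement about safety at completion answers a different question: what event rate the data support, and how it compares with the rates the plan calls baseline and excessive. Section 7.d uses one set of numbers for both, and gives no other numerical safety criterion.

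The nominal alpha and power of an SPRT assume that sampling continues until a boundary is reached. Here it ends at 25 infants. If the capped limits are rarely crossed even when the true rate is excessive, then data that contradict the plan's own baseline would still fall outside its definition of unsafe. A reader of the final report could take that as reassurance the data do not give.

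**Working it through.** **Inputs.** Alpha 0.05, power 80%, the three pairs of rates and the printed limits (section 7.d); n = 25 (Accrual).

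**Step 1: reproduce the limits.** The upper SPRT boundary is crossed at k events in n infants when k·ln(p1/p0) + (n − k)·ln((1 − p1)/(1 − p0)) ≥ ln(0.80/0.05) = ln 16 = 2.773. Solving for the largest n at each k:

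| Category | Events | Largest n, computed | Largest n, printed |
|---|---|---|---|
| Severe | 6, 7, 8 | 8, 18, 27 | 8, 17, 27 |
| Oxygen/flow | 5, 6, 7, 8 | 8, 13, 19, 24 | 8, 13, 18, 24 |
| Tactile | 4, 5, 6, 7 | 6, 14, 22, 31 | 6, 14, 22, 30 |

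The printed limits are reproduced to within one infant. The printed limits are used below.

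**Step 2: largest severe count that crosses nothing.** With ln(0.13/0.08) = 0.4855 and ln(0.87/0.92) = −0.0559:
- 7 of 25: 7 × 0.4855 − 18 × 0.0559 = 2.393, below 2.773, so not crossed.
- 8 of 25: 8 × 0.4855 − 17 × 0.0559 = 2.934, so crossed. It also meets the printed limit of 8 in the first 27.

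The largest uncrossed count is therefore 7, provided that at most 5 events fall in the first 8 infants and at most 6 in the first 17. There are C(25,7) = 480,700 orderings of 7 events. Of these, 19,448 have all 7 in the first 17, and a further 224 have 6 in the first 8 without all 7 in the first 17. That leaves 480,700 − 19,672 = 461,028, or 95.9%, that cross no limit. If the second limit were the computed 7 of 18, the share would be 93.3%.

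**Step 3: what 7 of 25 says.** The rate is 28.0%, exact 95% CI 12.1% to 49.4%. P(X ≥ 7) for n = 25 is 0.0028 at 8% and 0.036 at 13%. The one-sided 95% lower bound is 13.9%. So the result excludes the baseline and, on the one-sided bound, the excessive rate as well. The two-sided interval does include 13%.

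**Step 4: the other categories.**
- Oxygen/flow: 8 of 25 (32%) is uncrossed only if the eighth event is in infant 25 and the earlier limits are also missed. That is 28% of orderings; p = 0.011 against 13%.
- Tactile: 6 of 25 (24%) is uncrossed in 54% of orderings; p = 0.012 against 8%.

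**Step 5: chance of crossing any limit within 25 infants** (exact infant-by-infant recursion on the printed limits):

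| Category | At baseline | At excessive rate |
|---|---|---|
| Severe | 0.06% (8%) | 1.2% (13%) |
| Oxygen/flow | 1.2% (13%) | 26% (25%) |
| Tactile | 0.9% (8%) | 18% (17%) |

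For severe events at a true 25%, about three times baseline, the chance is 28%. The nominal 80% is not approached at any of the stated excessive rates.

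**Step 6: an exact one-sided 5% test at completion, for comparison.** The smallest counts with p ≤ 0.05 against baseline are 5 severe, 7 oxygen/flow and 5 tactile (p = 0.045, 0.036 and 0.045). Power at the plan's excessive rates is 22%, 44% and 42%. The chance of at least one false flag when all three baselines hold is about 12% (simulation with mutually exclusive categories).

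**The case against.** The strongest reply is that section 7.d is a monitoring plan. It nowhere says that a trial which crosses no limit will be declared safe, and section 6 announces no final safety classification. A reader might infer a formal end-of-trial verdict of safe, but the documents do not support that. They give a definition of unsafe and say nothing about its converse. What stands against the plan is that this definition is the only numerical safety criterion it has.

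A reader might also infer that infants are unprotected below the limits. They are not. The monitor may stop on judgment, weighing the estimated excess risk and the strength of the evidence, and 7 of 25 is the kind of result that wording covers. But that provision governs stopping and is not written into the definition of unsafe.

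It is tempting to blame repeated looks for the strictness of the limits. For severe events that is wrong: crossing has probability 0.06% at baseline, far below the nominal 5%, because an 8% versus 13% SPRT is truncated at 25 infants. Deleting the equating sentence does not repair that weakness; it only stops the limits from being read as a safety finding.

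Finally, the oxygen/flow and tactile examples depend much more on event order than the severe one, and a final test would itself miss most cases at the plan's own excessive rates. Both points are correct. They favour reporting estimates with intervals over imposing another binary label.

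**Conclusion.** The point holds and should be fixed. By the plan's own definition, 7 severe events in 25 infants is not unsafe in 96% of orderings, although it contradicts the 8% baseline (p = 0.003) and sits poorly with the 13% excessive rate (p = 0.036). Eight oxygen/flow events (28% of orderings) and six tactile events (54%) can also escape, less typically. With crossing probabilities of 0.06%, 1.2% and 28% at true severe rates of 8%, 13% and 25%, failure to cross carries little information about safety.

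This rests on four assumptions: all 25 infants are counted; each infant's event is counted in its own category only; the definition's reference to moderate or adverse events is meant to include the severe category; and the limit of 8 in the first 27 still applies to an eighth event by infant 25. A reader might take the remark about exceeding the sample size to switch that last limit off, in which case up to 14 of 25 severe events (6 in the first 17, then 8 in the last 8) could escape. The text does not say so, and 7 is the conservative figure.

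The primary length-of-stay analysis and the monitor's authority to stop are unaffected.

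**What to change.** In section 7.d, delete the sentence that equates unsafe with the stopping parameters, and reword the one before it so that the thresholds are described as stopping limits only. Add: *The limits above govern stopping only; not crossing them does not establish safety. At completion, the event rate in each category will be reported with its exact 95% confidence interval, beside the stated baseline and excessive rates.*

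The cost is two or three sentences and three intervals in the report. No stopping limit, procedure or sample size changes, and no error rate is affected.

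A formal end-of-trial test is optional. If the sponsor wants one at one-sided 5%, the thresholds are at least 5 severe, 7 oxygen/flow or 5 tactile events in 25. The plan should then disclose the power at its own excessive rates (22%, 44% and 42%) and the overall false-flag rate of roughly 12%. That is a real trade-off in an uncontrolled feasibility study whose baselines are given without a source, so leaving the test out is equally defensible.
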